1.3.4. Open-label Unblinding Visit (Prior to Amendment 7)

Visit #	Unblinding visit ^a	
	Unblinding	Vaccination ^b
Visit Window	Preferably no later than 2 months of local Protocol Amendment 5 approval	Preferably no later than 2 months of local Protocol Amendment 5 approval
Visit Type	On-site / Remote ^b	On-site
Informed reconsent ^b		●
Unblinding	●	
Body temperature ^c		●#
Urine pregnancy test ^d		●#
Nasal sample collection for SARS-CoV-2 testing ^e		●#
Blood sample for humoral immunogenicity and SARS-CoV-2 serology, mL ^f		●#10 mL
Clinical lab blood sample (whole blood), mL ^g		●#7 mL
Pre-vaccination symptoms ^h		●#
Vaccination ⁱ		●
Post-vaccination observation ^j		●
MAAE recording ^k	●	●
(S)AE recording ^l	●	●
Concomitant therapies ^m	●	●

pre vaccination

- After Ad26.COV2.S EUA in the US and approval of Protocol Amendment 4 by the local Health Authority and the IEC/IRB, all participants enrolled during the double-blind phase will be invited for an on-site unblinding visit and the study will continue as an open-label study. This visit is also applicable to participants already unblinded during the double-blind phase of the study. After the study pause, the unblinding visit can be done at a scheduled or unscheduled visit but preferably during a planned visit, within 2 months of the local approval of Amendment 5. If this is not operationally feasible, an unscheduled visit may be planned. If the unblinding visit is combined with a scheduled visit, the procedures of the scheduled visit should be completed as well, with the exception of solicited symptoms collection in the safety subset (please refer to Section 8.3.1 and Section 8.3.2). However, procedures that would be duplicated should be done only once. All participants will be encouraged to remain in the study and will be followed for efficacy, safety, and immunogenicity, as originally planned. All participants will be counselled to continue practicing other public health/preventive measures that were introduced at the start of this pandemic (eg, social distancing, face masks, frequent hand washing), in compliance with local and national guidelines. After the unblinding visit, participants will resume procedures depicted in Schedule of Activities, Section 1.3.3.
- Signing of the ICF should be done before any visit-related procedure. In case the unblinding occurs remotely, participants should be provided with the ICF, the investigator will review the content with the participant, and the ICF should be signed electronically or at the next on-site study visit. Investigators will be encouraged to follow local health authority guidelines on prioritization of immunization.
- Body temperature will be measured preferably via the oral route, or in accordance with the local standard of care.
- For participants of childbearing potential only. Applicable for participants who will receive vaccination at the unblinding visit. Participants who are pregnant and previously received placebo during the double-blind phase may be vaccinated with Ad26.COV2.S (single-dose regimen), if allowed by local regulations for emergency use of vaccines and if the investigator considers that the potential benefits outweigh any potential risks to the mother and fetus (see Section 6.4).

- e. Diagnostic molecular RT-PCR test for SARS-CoV-2 infection (from nasal swab) will be performed by a central laboratory. This sample should be collected in all participants and should not be tested locally.
- f. Blood sample for humoral immunogenicity and sero-confirmation of SARS-CoV-2 infection. Blood sample should be taken except when the previous sample for assessment of humoral immunogenicity and sero-confirmation of SARS-CoV-2 infection occurred within 5 days of the visit. These results will not be available in real time, and this cannot be used to inform participants at the time of visit. If the visit is combined with a scheduled visit (Section 1.3.3) that comprises a blood sample, only the blood sample from the scheduled visit should be collected.
- g. Whole blood samples will be used for immediate measurement of a platelet count (as part of a complete blood count, if applicable) in a local laboratory or substitute for local laboratory, depending on local feasibility towards turnaround time of sample processing. Serum samples will be derived from the whole blood sample and stored for potential future coagulation-related testing in a central laboratory if the participant experiences a suspected AESI (see Section 10.2, Appendix 2). If a whole blood sample has been taken within 5 days before vaccination and platelet results are available, sample collection does not need to be performed before vaccination.
- h. Investigator must check for acute illness or body temperature $\geq 38.0^{\circ}\text{C}/100.4^{\circ}\text{F}$ at the time of vaccination. If any of these events occur within 24 hours prior to the planned vaccination, the vaccination can be rescheduled as long as this is within the allowed window. If the vaccination visit cannot be rescheduled within the allowed window or the contraindications to vaccination persist, the sponsor should be contacted for further guidance.
- i. Participants who initially received either one dose or two doses of placebo will be offered to receive a single dose of Ad26.COV2.S, under the conditions delineated in Section 6.4. Participants from the Ad26.COV2.S arm will receive their second dose under the conditions delineated in Section 6.4.
- j. The observation period for participants who will receive vaccination must be at least 15 minutes, except where local regulations require a longer observation period (eg, Belgium), after vaccination in the study. Participants who will receive vaccination will be allowed to leave the study site after it is documented that the post-vaccination observation period is complete.
- k. MAAEs are to be reported for all participants from the moment of the 1st vaccination until 6 months after the last double-blind or open-label vaccination, except for MAAEs leading to study discontinuation which are to be reported during the entire study. New onset of chronic diseases will be collected as part of the MAAEs.
- l. All (S)AEs related to study procedures or non-investigational sponsor products will be reported from the time a signed and dated ICF is obtained until the end of the study/early withdrawal. All other SAEs are to be reported from the moment of vaccination until completion of the participant's last study-related procedure. AEs leading to study discontinuation or discontinuation of study vaccination (regardless of the causal relationship) are to be reported from the moment of the 1st vaccination until completion of the participant's last study-related procedure. Applicable from the time of local approval of Protocol Amendment 5 onwards: Suspected AESIs are to be reported from the moment of vaccination until completion of the participant's last study-related procedure (see Section 8.3.1). Special reporting situations, whether serious or non-serious, are to be recorded for each vaccination from the time of vaccination until 28 days post-vaccination (applicable for both double-blind and open-label). Participants will be reminded once a month to contact the study site in case of an SAE.
- m. Refer to Section 6.10 for collection and recording of concomitant therapies associated with SAEs, suspected AESIs, and MAAEs.
- n. For those who do not need to receive further vaccination at the time of the unblinding visit (see Section 6.4), all activities (except those related to vaccination) need to be performed to comply with the required reconsent, blood and swab sampling, and safety evaluations.

AE = adverse event; AESI = adverse event of special interest; EUA = Emergency Use Authorization; d = day(s); ICF = informed consent form; MAAE = medically-attended adverse event; SAE = serious adverse event; SARS-CoV-2 = severe acute respiratory syndrome coronavirus-2.

1.3.5. Booster Vaccination Visit

With implementation of Protocol Amendment 6, all ongoing participants who received only a single Ad26.COV2.S vaccination in the study will be offered a single booster Ad26.COV2.S vaccination, under the conditions delineated in Section 6.5. Participants who already received 2 vaccinations with Ad26.COV2.S at the 5×10^{10} vp dose level or any COVID-19 vaccinations outside of the study (including the Janssen vaccine) at the time of local approval of Protocol Amendment 6 are not eligible to receive a booster vaccination with Ad26.COV2.S.

As of Protocol Amendment 7, no further booster vaccination will be provided unless there is a medical reason or if there is a non-availability of other vaccines to the participant (and prior to vaccine expiry date at the study site level). The investigator should counsel on possible vaccination outside of the study.

Visit #	Booster Vaccination Visit ^a
Visit Timing and Window	Preferably Vac 1 + 6-12 months Minimally Vac 1 + 3 months
Informed reconsent ^b	● [#]
Body temperature ^c	● [#]
Pre-vaccination symptoms ^d	● [#]
Urine pregnancy test ^e	● [#]
Nasal sample collection for SARS-CoV-2 testing ^f	● [#]
Blood sample for humoral immunogenicity and SARS-CoV-2 serology, mL ^g	● [#] 10 mL
Clinical lab blood sample (whole blood) ^h	● [#] 7 mL
Vaccination ⁱ	●
Post-vaccination observation ^j	●
(S)AE, MAAE and suspected AESI recording ^k	●
Concomitant therapies ^l	●

[#] procedure to be completed pre-vaccination

- The Booster Vaccination Visit should occur preferably within 6-12 months after first Ad26.COV2.S vaccination. If this is not possible, the booster vaccination should not occur earlier than 3 months after first Ad26.COV2.S vaccination. The Booster Vaccination Visit should preferably coincide with the participant's next scheduled visit (ie, Visit 7 or Visit 8 for the majority of participants) from the original schedule in Section 1.3.3. If not operationally feasible to coincide with an existing visit, an unscheduled visit may be planned. If the Booster Vaccination Visit coincides with a scheduled visit, the procedures of the scheduled visit should be completed as well. However, procedures that would be duplicated should be done only once. All participants will be encouraged to remain in the study and will be followed for efficacy, safety, and immunogenicity, as originally planned. All participants will be counselled to continue practicing other public health/preventive measures that were introduced at the start of this pandemic (eg, social distancing, face masks, frequent hand washing), in compliance with local and national guidelines. After the Booster Vaccination Visit, participants will resume procedures and visits depicted in Schedule of Activities, Section 1.3.3.
- Signing of the ICF should be done before any visit-related procedures are performed.
- Body temperature will be measured preferably via the oral route, or in accordance with the local standard of care.

- d. Investigator must check for acute illness or body temperature $\geq 38.0^{\circ}\text{C}/100.4^{\circ}\text{F}$ at the time of vaccination. If any of these events occur within 24 hours prior to the planned vaccination, the vaccination can be rescheduled as long as this is within the allowed window.
- e. For participants of childbearing potential only. Note: Participants who are pregnant and previously received the open-label vaccination may receive the booster vaccination, if allowed by local regulations for use of the vaccines and if the investigator considers that the potential benefits outweigh any potential risks to the mother and fetus.
- f. Up to Protocol Amendment 7, diagnostic molecular RT-PCR test for SARS-CoV-2 infection (from nasal swab) will be performed by a central laboratory. This sample should be collected in all participants and should not be tested locally.
- g. Up to Protocol Amendment 7, blood sample for humoral immunogenicity and sero-confirmation of SARS-CoV-2 infection. Blood sample should be taken except when the previous sample for assessment of humoral immunogenicity and sero-confirmation of SARS-CoV-2 infection occurred within 5 days of the visit. These results will not be available in real time, and this cannot be used to inform participants at the time of visit. If the visit is combined with a scheduled visit (Section 1.3.3) that comprises a blood sample, only the blood sample from the scheduled visit should be collected.
- h. Whole blood samples will be used for immediate measurement of a platelet count (as part of a complete blood count, if applicable) in a local laboratory or substitute for local laboratory, depending on local feasibility towards turnaround time of sample processing. Serum samples will be derived from the whole blood sample and stored for potential future coagulation-related testing in a central laboratory if the participant experiences a suspected AESI (see Section 10.2). If a whole blood sample has been taken within 5 days before vaccination and platelet results are available, sample collection does not need to be performed before vaccination.
- i. With implementation of Protocol Amendment 6, all ongoing participants who received only a single Ad26.COV2.S vaccination in the study will be offered to receive a single Ad26.COV2.S booster vaccination, under the conditions delineated in Section 6.5. Participants who already received 2 vaccinations with Ad26.COV2.S at the 5×10^{10} vp dose level or any COVID-19 vaccinations outside of the study (including the Janssen vaccine) at the time of local approval of Protocol Amendment 6 are not eligible to receive a booster vaccination with Ad26.COV2.S.
- j. The observation period for participants who will receive vaccination must be at least 15 minutes, except where local regulations require a longer observation period (eg, Belgium), after vaccination in the study. Participants who will receive vaccination will be allowed to leave the study site after it is documented that the post-vaccination observation period is complete.
- k. All (S)AEs related to study procedures or non-investigational sponsor products will be reported from the time a signed and dated ICF is obtained until the end of the study/early withdrawal. All other SAEs and all AEs leading to study discontinuation or discontinuation of study vaccination are to be reported from the moment of first vaccination until completion of the participant's last study-related procedure. Participants will be reminded once a month to contact the study site in case of an SAE. Special reporting situations, whether serious or non-serious, are to be recorded for each vaccination from the time of vaccination until 28 days post-vaccination. MAAEs are to be reported from the moment of the 1st vaccination until 6 months after the last vaccination (including the open-label vaccination or booster vaccination, whichever comes last), except for MAAEs leading to study discontinuation which are to be reported during the entire study. New onset of chronic diseases will be collected as part of the MAAEs. Suspected AESIs are to be reported from the moment of vaccination until completion of the participant's last study-related procedure or (as of Amendment 7) phone call/study contact (see Section 1.3.7).
- l. Refer to Section 6.10 for collection and recording of concomitant therapies associated with (S)AEs, MAAEs, and suspected AESIs.

AE = adverse event; AESI = adverse event of special interest; d = day(s); ICF = informed consent form; MAAE = medically-attended adverse event; SAE = serious adverse event; SARS-CoV-2 = severe acute respiratory syndrome coronavirus-2.

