A single dose of Ad26.COV2.S vaccine is immunogenic and highly efficacious against severe COVID-19 disease and COVID-19 related hospitalization and death. Furthermore, while protection against variants of concern (such as the Beta and Mu variants in study COV3001 and the Delta variant in the Sisonke study³⁷) remains high against serious disease, hospitalization, and death, this protection is lower against, eg, the Gamma variant compared to the reference Wuhan strain. Protection against severe/critical disease caused by different variants of concern (such as Gamma, Lambda and Mu variants) was shown to be reduced in the final analysis of study COV3001 compared to the reference Wuhan strain and the Alpha variant, for example. Giving a second dose of Ad26.COV2.S results in marked increases of immune responses and those higher immune responses correlate with better protection against COVID-19, as shown in the primary analysis of study COV3009.⁴⁴ Some national vaccination recommendation bodies (eg, CDC²⁰) have recently advised to give a booster vaccination. Therefore, this amendment will permit boosting of all eligible ongoing participants in this study who received only a single vaccination with Ad26.COV2.S in the study. As the Janssen vaccine is approved as a single dose vaccine, participants who received two doses of Ad26COV2.S are considered to already have received the booster dose. Given that the sponsor has no safety information on mixed schedule vaccinations,

participants that received a COVID-19 vaccination outside of the study will not be offered the booster dose in this study.

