5. STUDY POPULATION

Screening for eligible participants will be performed within ≤ 28 days before randomization and 1st administration of the study vaccine, or on the day of the 1st vaccination. Refer to Section 5.4 for conditions under which the repeat of any screening procedures are allowed.

The inclusion and exclusion criteria for enrolling participants in this study are described below. Some inclusion and exclusion criteria only apply to a particular stage (1 or 2), as indicated below.

See Section 4.1 for more details about enrollment in the different stages. If there is a question about these criteria, the investigator must consult with the appropriate sponsor representative and resolve any issues before enrolling a participant in the study. Waivers are not allowed.

Once enrolled, participants who received placebo during the double-blind phase will be eligible to receive a single dose of vaccination with Ad26.COV2.S (open-label dose) in the open-label phase if they agree and consent to receive the active vaccine and meet the criteria described in Section 6.4. Eligibility criteria to receive the booster vaccination are described in Section 6.5.

Following approval of Protocol Amendment 4 and start of the open-label phase, newly enrolled participants must meet the stage 2 criteria in Sections 5.1 and 5.2.

For a discussion of the statistical considerations of participant selection, refer to Section 9.2.

5.1. Inclusion Criteria for the Double-blind Phase and for Newly Enrolled Participants in the Open-label Phase^a

Each potential participant must satisfy all of the following criteria to be enrolled in the study:

1. Participants must provide consent indicating that he or she understands the purpose, procedures and potential risks and benefits of the study, and is willing to participate in the study.
2. Participant is willing and able to adhere to the prohibitions and restrictions specified in this protocol.
 3. Criterion modified per Amendment 2
 - 3.1 Criterion modified per Amendment 6
 - 3.2 Participant is ≥ 18 to <60 years or ≥ 60 years of age on the day of signing the ICF. Vaccine administration/recruitment in each age group may change per country based on national recommendation. The investigator should contact the sponsor prior to any change to vaccine administration/recruitment.
4. Criterion modified per Amendment 1:
 - 4.1 Criterion modified per Amendment 2:
 - 4.2 Criterion modified per Amendment 3:

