2. Participant has a known or suspected allergy or history of anaphylaxis or other serious adverse reactions to vaccines or their excipients (including specifically the excipients of the study vaccine; refer to the IB).
3. Criterion modified per Amendment 2:
 - 3.1 Criterion modified per Amendment 4:
 - 3.2 Participant has abnormal function of the immune system resulting from:
 - a. Clinical conditions (eg, autoimmune disease or potential immune mediated disease or known or suspected immunodeficiency, or patient on hemodialysis) expected to have an impact on the immune response of the study vaccine. Participants with clinical conditions stable under non-immunomodulator treatment (eg, autoimmune thyroiditis, autoimmune inflammatory rheumatic disease such as rheumatoid arthritis) may be enrolled at the discretion of the investigator. Non-immunomodulator treatment is allowed as well as steroids at a non-immunosuppressive dose or route of administration^b.
 - b. Chronic or recurrent use of systemic corticosteroids within 6 months before administration of the 1st dose of study vaccine and during^a the study. A substantially immunosuppressive steroid dose is considered to be ≥ 2 weeks of daily receipt of 20 mg of prednisone or equivalent.
Note: Ocular, topical, inhaled, or injectable corticosteroids for local use are allowed.
 - c. Administration of antineoplastic and immunomodulating agents or radiotherapy within 6 months before administration of the 1st dose of study vaccine and during the study^a.
Note: Non-immunomodulating monoclonal antibodies (after discussion with Sponsor study physician) are allowed.
4. Criterion modified per Amendment 3:
 - 4.1 Participant received treatment with Ig in the 3 months or exogenous blood products (autologous blood transfusion are not exclusionary) in the 4 months before the planned administration of the 1st dose of study vaccine or has any plans to receive such treatment during the study^a.
5. Participant received or plans to receive:

^a Eligibility criteria for the open-label and the booster vaccination are described in Section 6.4 and Section 6.5, respectively.

^b No longer applicable as of first date of Protocol Amendment 7.

- a. Licensed live attenuated vaccines within 28 days before or after planned administration of the 1st or subsequent study vaccinations.
- b. Other licensed (not live) vaccines within 14 days before or after planned administration of the 1st or subsequent study vaccinations.

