Participants may be unblinded upon their request to receive a different authorized/licensed COVID-19 vaccine. Investigators may receive requests to unblind study participants who become eligible to receive another authorized/licensed COVID-19 vaccine outside of the study if/when these become available. In these cases, the investigator will discuss with the participant available options and ramifications, including whether they are eligible to receive the Ad26.COV2.S vaccine in the study during the unblinding study visit. The reason for the unblinding request should be documented. The name and date(s) of administration of the other COVID-19 vaccine should be recorded (see Section [6.10](#)).

If it is determined that the participant received the Ad26.COV2.S vaccine (and not placebo), the participant will be informed that there are no data on the safety of receiving two different COVID-19 vaccines and no further study vaccination would be permitted in the event he/she chooses to receive the vaccine outside the study. Unblinded participants, whether in the vaccine or control group, will be asked to continue to be followed in this study in line with the [Schedules of Activities](#). Safety, efficacy, and immunogenicity evaluations will be identical for all participants, including participants that are unblinded to obtain an authorized/licensed COVID-19 vaccine and who remain in the study. All data will be analyzed separately from the point of unblinding for safety, efficacy and immunogenicity, as described in the Statistical Analysis Plan.

Participants who opt for enrollment in an Expanded Access Program or a Phase 3b study (eg, Sisonke/TOGETHER in South Africa) may be unblinded upon their request and will be encouraged to continue in the VAC31518COV3009 study. Study investigators should query participants to elicit and document such participation in other studies in the VAC31518COV3009 eCRF including the vaccination.

Once Protocol Amendment 4 is approved, participants who were previously unblinded (under previous amendments) because they were offered another approved/licensed vaccine will follow the procedures detailed in Section 6.4 and Section 8.8.

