6.5. Booster Vaccination

With implementation of Protocol Amendment 6, all ongoing participants who received only a single vaccination with Ad26.COV2.S in the study will be offered a single booster dose of Ad26.COV2.S vaccine (5×10^{10} vp), as indicated in the SoA in Section 1.3.5. Participants who already received 2 vaccinations with Ad26.COV2.S at the 5×10^{10} vp dose level or any COVID-19 vaccinations outside of the study (including the Janssen vaccine) at the time of local approval of

Protocol Amendment 6 are not eligible to receive a booster vaccination with Ad26.COV2.S. The booster vaccination will be administered in the open-label phase of the study, preferably within 6 to 12 months after the participant's first Ad26.COV2.S vaccination in the study. If this is not possible, the booster vaccination should not occur earlier than 3 months after the participant's first Ad26.COV2.S vaccination. The Booster Vaccination Visit should preferably coincide with the participant's next scheduled visit (ie, Visit 7 or Visit 8 for the majority of participants) from the original SoA in Section 1.3.3 and should not occur after the expiry date of the Ad26.COV2.S vials available at the site. If not operationally feasible to coincide with an existing visit, an unscheduled visit may be planned. After the Booster Vaccination Visit, participants will continue procedures and visits as in the original SoA. All participants (whether they consent to the booster vaccination or not) will be encouraged to remain in the study and will be monitored for safety, immunogenicity, and efficacy according to their original schedule.

Participants may be offered the single booster dose of Ad26.COV2.S vaccine under the following special conditions:

- Participants, who had met vaccination discontinuation criteria under previous amendments, will be offered a single booster dose of Ad26.COV2.S vaccine at the discretion of the investigator, except the following participants, who:
 - withdrew consent from the study or,
 - received any COVID-19-related experimental medication (including any experimental vaccines other than the study vaccine) or,
 - previously experienced TTS or heparin-induced thrombocytopenia (HIT) or,
 - previously experienced CLS or,
 - are planning to receive another COVID-19 vaccine within the 3 months after the booster vaccination.

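### The booster rule in Section 6.5 fixes outside COVID-19 vaccination status at local approval of Amendment 6 rather than at dosing, which is narrower than the safety reason in Section 2.1

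*Protocol*

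**What the plan says.** Section 5 makes Section 6.5 the governing text: "Eligibility criteria to receive the booster vaccination are described in Section 6.5". Footnotes to Sections 5.1 and 5.2 repeat this: "Eligibility criteria for the open-label and the booster vaccination are described in Section 6.4 and Section 6.5, respectively".

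Section 6.5 opens with the offer: "all ongoing participants who received only a single vaccination with Ad26.COV2.S in the study will be offered a single booster dose". Its next sentence removes participants who already have two Ad26.COV2.S doses at the study dose level, and it deals with outside vaccination as follows: "any COVID-19 vaccinations outside of the study (including the Janssen vaccine) at the time of local approval of Protocol Amendment 6 are not eligible". Section 1.3.5 carries the same rule.

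Section 2.1 explains why the exclusion exists: "Given that the sponsor has no safety information on mixed schedule vaccinations". It concludes that "participants that received a COVID-19 vaccination outside of the study will not be offered the booster dose in this study". No date is attached there, although an earlier paragraph of Section 2.1 repeats the dated rule.

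Section 6.3, on Ad26.COV2.S recipients who are unblinded so that they can take another vaccine, is also undated: "no further study vaccination would be permitted in the event he/she chooses to receive the vaccine outside the study".

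On timing, Section 1.3.5 prefers that the booster coincide with the participant's "next scheduled visit (ie, Visit 7 or Visit 8 for the majority of participants". As of Amendment 7, Sections 1.3, 1.3.5, 5.5 and 6.5 stop boosting with two exceptions: a medical reason had earlier prevented the dose, or no other vaccine is available to the participant.

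**The concern.** The exclusion has a stated safety purpose: the sponsor has no safety data on mixing Ad26.COV2.S with other COVID-19 vaccines. Whether that purpose applies to a person depends on what the person has received by the day of dosing. The governing sentence asks instead what had been received by an administrative date that precedes dosing and differs by place. Someone vaccinated elsewhere between the two dates meets the letter of the eligibility text and fails its rationale.

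At stake is a booster given in a combination that the protocol meant to avoid, without any breach of Section 6.5. This concerns eligibility and safety. No hypothesis test, power figure or sample size depends on it.

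**Working it through.** The plan gives no figure to reproduce, so this is mainly a comparison of texts.

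**1. The offer.** Section 6.5 counts only doses given in the study. An outside vaccination therefore does not take a one-dose participant out of the offer. Only the exclusion sentence can do that.

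**2. The exclusion, by date of the outside vaccination.**

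| Outside vaccination received | Section 6.5 and repeats | Section 2.1, undated statement |
|---|---|---|
| By local approval of Amendment 6 | Excluded | Excluded |
| After local approval, before the booster | Not excluded | Excluded |

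The second row is the gap.

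**3. Does other text close it?**
- *The exception list in Section 6.5* names experimental COVID-19 products and a vaccine planned for the 3 months after the booster. It does not name an authorized vaccine already received. It also only qualifies a relaxation for people who had met discontinuation criteria under previous amendments.
- *Section 6.3* covers Ad26.COV2.S recipients unblinded to take another vaccine. It does not address placebo recipients who crossed over and hold one open-label dose.
- *Section 6.4* lists an outside vaccination as a bar, but for placebo-arm participants before their open-label dose.
- *Exclusion criterion 7 in Section 5.2* disallows other coronavirus vaccines during the study. It covers vaccines other than Ad26.COV2.S, so it misses an outside Janssen dose, which the booster rule names. Its footnote says that it lapses at Amendment 7.
- *The booster visit schedule in Section 1.3.5* marks several items as pre-vaccination (reconsent, temperature, symptoms, pregnancy test, samples). A check of outside vaccination is not among them. Concomitant therapies are not marked pre-vaccination, and the footnote ties them to adverse events.

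**4. How long the uncovered interval could be.** Inputs from Section 1.3.3: Visit 7 is Visit 4 + 24 weeks (window -106 to +28 days); Visit 8 is Visit 4 + 52 weeks (window ±21 days). Take a hypothetical participant whose Visit 7 falls just before local approval and who is boosted at Visit 8:
- nominal: 52 - 24 = 28 weeks = 196 days
- shortest: 196 - 28 - 21 = 147 days
- longest: 196 + 106 + 21 = 323 days

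An unscheduled booster visit could bring the interval close to 0. These figures are visit spacing for one constructed case. They do not measure how many people were exposed or harmed.

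**5. What remains under Amendment 7.** The non-availability exception hardly fits someone who has just been vaccinated elsewhere. The medical-reason exception can fit, and Section 1.3.5 also tells the investigator to counsel on vaccination outside the study.

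**The case against.** The strongest reply is that the protocol's intent is plain and that a sensible site would not boost such a participant. Section 2.1 says so without a date, Section 6.3 says so for one group, Section 6.4 treats outside vaccination as a reason to stop study vaccination, and before Amendment 7 the criterion in Section 5.2 disallowed most outside vaccines. Someone vaccinated elsewhere after approval of Amendment 6 might also meet a current discontinuation criterion in Section 7.1, where the relaxation for earlier amendments gives no help. The available text ends within Section 6.10, so Sections 7.1 and 8.9 could not be checked. Either may hold the missing rule or check.

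Much of this stands as a limit on weight. It does not remove the point: Section 5 sends the reader to Section 6.5 for eligibility, and that section has the wrong reference date.

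Three stronger readings are tempting and are not supported:
- *That the sections flatly contradict each other.* Section 2.1 carries both the dated and the undated rule, so this is an inconsistent cut-off.
- *That the protocol shows it happened.* Section 2.1 reports that many placebo participants did not cross over, for example because they took another vaccine. Those people had no in-study Ad26.COV2.S dose and so lie outside the booster offer. The remark says nothing about one-dose participants.
- *That results are compromised.* Section 3 makes the open-label analyses descriptive and reports outside-vaccinated participants as a separate cohort. The double-blind primary analysis is untouched.

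**Conclusion.** The point holds as a minor one. The governing eligibility sentence takes outside-vaccination status at local approval of Amendment 6, while the protocol's own safety reason requires status at dosing. Read literally, it leaves in the offer a one-dose participant vaccinated elsewhere in between.

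Under the current amendment the practical reach is small: the few boosters still allowed, chiefly under the medical-reason exception. The number affected cannot be derived from the protocol, and it is zero if every site followed the undated statement in Section 2.1. The conclusion rests on a literal reading of Section 6.5 and on Sections 7.1 and 8.9 not already closing the gap.

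**What to change.** In Section 6.5, keep the bar on participants with two Ad26.COV2.S doses. For outside COVID-19 vaccination (the Janssen vaccine included), replace the approval date with *at any time before the booster vaccination*. Align the repeats. The sentence stands in 12 places: four in Section 1.1, one in 1.2, one in 1.3.3, two in 1.3.5, one in 2.1, two in 4.1 and one in 6.5 (4 + 1 + 1 + 2 + 1 + 2 + 1 = 12). Section 6.5 is the essential one.

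Unless Section 8.9 already requires it, have the site confirm outside-vaccination status before any booster still given under the Amendment 7 exceptions.

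The cost is one reworded sentence and one question to the participant before dosing. For participants unblinded to take another vaccine, Section 6.3 already has its name and date recorded. No visit, sample or change in sample size is needed.
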